## SCHEDULE OF EVENTS

Procedures	Eligibility Screening	Baseline Testing	Intervention	3-Month Testing	6-Month Testing	9-Month check-in	12-Month Testing	Monthly - Month 1 – 12
Pre-screening eligibility	X							
Consent form	X							
Exercise (intervention)			X					
Dyadic Coping		X		X	X		X	
Emotional intimacy - DAS		X						
Concealment of symptoms – EIDB Scale		X		X	X		X	
Physical intimacy – The Physical Intimacy Behavior Scale		X		X	X		X	
Pain - BPI		X		X	X		X	
Fatigue - FACIT		X		X	X		X	
Depressive symptoms – CES-D		X		X	X		X	
PROMIS Anxiety		X		X	X		X	
Fear of recurrence – F.O.R. scale		X		X	X		X	
Demographics – demographic questionnaire		X						
Comorbidities – Charlson Comorbidity Index		X		X	X		X	
Shared activities		X		X	X		X	
Physical activity - CHAMPS		X		X	X		X	
Quality of Life – QLQ-C30 & SF-36		X		X	X		X	
Sexual Satisfaction – PROMIS Sexual Satisfaction Survey		X		X	X		X	
Care strain – Role Overload; Multidimensional caregiver strain index (MCSI)		X		X	X		X	
Cancer-related Loneliness – Cancer Loneliness Scale		X		X	X		X	
Post-Intervention Survey					X			
Inflammation & cardiovascular health--blood draw		X		X	X		X	
Exercise Follow-up Survey						X	X	
Adverse Event Survey								X
Body composition-DXA		X		X	X		X	
Resting Blood Pressure		X		X	X		X	

Procedures	Eligibility Screening	Baseline Testing	Intervention	3-Month Testing	6-Month Testing	9-Month check-in	12-Month Testing	Monthly - Month 1 – 12
Physical functioning-PPB, iSWAY, 6-minute walk		X		X	X		X	
Muscle strength-1RM leg & bench press		X		X	X		X	
Push-up test*		X		X	X		X	
Plank test*		X		X	X		X	

\*Conducted during remote testing visits. For validity purposes, these measures may also be completed in the testing lab when in-person contact resumes.

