#### **Six-Month Follow-Up Period**

To evaluate the persistent effects of *Exercising Together* on individual and relationship health, all couples will be followed for an additional 6 months after formal training stops. Couples may wish to maintain their exercise habits or participate in shared activities other than exercise after formal training stops and we will not discourage them from doing so. To provide couples in supervised programs a resource to continue to engage in exercise after supervised training stops we will provide them with a DVD of their programs to use at home. During the last month of supervised training we will prepare participants for the transition to unsupervised training with discussions about behavioral strategies to stay active. We will assess participation in exercise and shared activities at 9 & 12 months and consider these behaviors in analysis for Aim 3 (see **Analysis Plan**). We will also repeat all measures at month 12 in order to better assess the residual effects of *Exercising Together* among couples that do or do not continue to exercise or engage in shared activities in the follow-up period.

**Participant safety.** None of our participants have dropped out of a study due to an injury related to exercise training; however, as with any study in older adults, exercise adherence has been affected by minor musculoskeletal complaints that usually stem from pre-existing orthopedic conditions. We will reduce the risk of injury and symptoms that might limit exercise adherence by: 1) required physician clearance for every participant and 2) monitoring and early care of musculoskeletal symptoms. If a survivor develops metastatic disease during the study his/her data from the point of the diagnosis will be considered separately, but s/he could continue in the study program with physician clearance.

**Participant Incentives:** Remuneration will be provided to couples based on completion of each study related activity as outlined in the table below, at each of the four main time points (baseline, 3-months, 6-months, and 12-months).

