### **Measures and Data Collection**

Outcomes data will be collected at 0 (baseline, just prior to randomization), 3 (mid-intervention), 6 (post-intervention), and 12 months (6 mos. after completion of the intervention (follow-up)). Written surveys are completed on a computer at the testing facility at baseline and online for follow-up visits. All measures are completed by both members of the couple at each wave.

Primary Outcome Measure:

1. Dyadic coping

Measured by the Relationship Focused Coping Scale to assess the degree with which couples practice active engagement and protective buffering using questions on a scale from 1 (never) to 5 (very often).

[Time Frame: 0 baseline (just prior to randomization), 3, 6, and 12 months]

2. Emotional intimacy

Measured by the Dyadic Adjustment Scale (DAS) to assess each partner's satisfaction with their relationship by answering questions on a 6-point scale ranging from 1(always agree) to 6 (always disagree).

[Time Frame: 0 baseline (just prior to randomization), 3, 6, and 12 months]

3. Physical intimacy

Measured by the Physical Intimacy Behavior scale which asks participants the frequency that they engage in, initiate, and avoid intimate behaviors using questions on a scale from 1 (none of the time) to 4 (most or all of the time).

[Time Frame: 0 baseline (just prior to randomization), 3, 6, and 12 months]

4. Concealment of symptoms

Measured by the Emotional-Intimacy Disruptive Behavior Scale. Patients report the extent to which they engage in 8 behaviors using a scale from 1 (rarely or none of the time) to 4 (most or all of the time).

[Time Frame: 0 baseline (just prior to randomization), 3, 6, and 12 months]

5. Symptom incongruence

Measured by the degree of agreement between the survivor and spouse/partner ratings of the survivor's pain, fatigue and physical function in the past week using the following instruments: the Brief Pain Inventory (BPI) to measure pain intensity and pain interference, Functional Assessment in Chronic Illness Therapy (FACIT) fatigue survey to measure fatigue, and perceived physical function using a subscale of the SF-36 medical outcomes survey (all described below).

[Time Frame: 0 baseline (just prior to randomization), 3, 6, and 12 months]

Secondary Outcome Measure:

6. Body composition

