Study visits may be delivered in-person with additional precautions during periods of hospital recommendations for decreased in-person contact, and/or delivered remotely via video conferencing. In order to determine the validity of remote delivery, participants may be asked to complete both sets of testing at every time point (in-person plus remote). In such cases remuneration will be offered to offset the additional time asked of participants. If delivered remotely, select testing measures will be adapted to this type of delivery. These testing measures include:

1. Height (self-report collected if in-person assessment not expected)
2. Weight
3. Physical Performance Battery (PPB) (see 11. Objective physical function above, under Secondary Outcome Measures)
4. All surveys (see 1-5 above, under Primary Outcome Measures, and 12-17 under Secondary Outcome Measures and Other Pre-specified Outcome Measures) will continue to be sent out electronically as previously described. If a participant needs a paper survey to complete the survey, one will be provided or their data will be marked as "missed" if study staff are unable to mail a paper survey to the participant during their outlined testing window.

To assess upper body strength remotely, novel assessments to this trial will include:

5. Push-up test  
Measured by the number of push-ups completed in one continuous bout until fatigue
6. Plank test  
Measured by the amount of time in seconds that the participant is able to hold a plank position

The following measures will not be collected remotely:

1. DXA scan (see 6. Body composition above, under Secondary Outcome Measures)
2. Resting blood pressure and blood draw (see 7-10. Cardiovascular health/Inflammation above, under Secondary Outcome Measures)
3. Postural and dynamic stability (see Additional Outcomes above)
4. 1-repetition maximum testing for leg press and bench press (see process outcomes above)

Ancillary study: All study visits will be conducted remotely via videoconferencing. Measures will be collected in accordance with remote testing procedures described above.

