Interested participants will be screened either by phone or in person using an IRB approved screening script. After initial screening, interested and eligible couples will come to the OHSU Knight Cancer Research Building and will be presented with an online IRB-approved Consent Form prior to any study-related procedure. The Consent Form will describe the goals of the study, study procedures, confidentiality, risks, benefits, and voluntary nature of the research. After participants view the consent online, and click the box that they have read and agree to participate (indicating that they have signed the consent), they will be sent links and requested to complete REDCap surveys. For the baseline testing session, couples will be asked to provide a fasting blood draw (which may be completed at an appointment separate of the baseline consenting visit but prior to initiation of the intervention), blood pressure, DXA scan, physical tests (PPB, 1RM leg and bench press, standing balance, and 6 minute walk test), and questionnaires. The testing session will take ~2-3 hours per couple, initially, and will be repeated at 3, 6, & 12 months and only take 1-2 hours. Following baseline testing, the Project Director will provide each couple with an envelope that contains their random assignment to a study group in order to retain blinding of the research assistants who conduct testing. Couples will be randomly assigned to 1 of 3 groups: 1) *Exercising Together*, 2) *Separate survivor / spouse/partner group exercise* 3) *Separate survivor / spouse/partner home exercise*. Enrollment will be stratified by cancer type and average couple age (<60 vs. 60-80). Assignment will be in random blocks of 6-9 couples for even enrollment.

During periods of hospital recommendations for decreased in-person contact, re-consent for the modified procedures will be done over the phone or via teleconference. Study team members will inform the participants of the modified procedures and note their verbal agreement to continue on the study.

Individuals who have not previously consented will be screened by phone or teleconference using an IRB approved screening script. After initial screening, interested and eligible couples will

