## 13.0 BIO-STATISTICAL CONSIDERATIONS

### Power and Sample Size

Required sample size was derived for the outcomes of Aim 1. Power analysis using traditional assumptions of the repeated measures ANOVA model suggest that as few as 174 couples would be necessary to detect a small effect ( $d=.20$ ) between groups over time, an effect smaller than the observed effect on affectionate behavior in spouses/partners in our previous work[40]. However, these traditional power calculations are known to be optimistic. While there are good power formulae for MLM clustered designs and repeated measures designs, as yet there is no specific formula for calculating power for dyadic analyses. Using a formula provided by Raudenbush and Bryk[104, 105] for individual repeated measures and estimates from our previous dyadic models, we calculate a sample of 264 couples measured 4 times over a 12-month period has a power of 0.80 to detect a moderate effect ( $d=.40$ ) on change over time. As dyad models using MLM control for interdependence between members of the couple, power is increased over an individual model. We, therefore, believe this to be a more conservative estimate of power. Further attempts to increase power and reduce Type I error will be to use the omnibus hypothesis-testing procedure in the HLM program. Another rule-of-thumb is to require a minimum number of subjects per parameter estimated. Even in the most complicated model, the proposed sample of 264 couples would exceed the minimum standard of 5-10 subjects per parameter estimated.[106] No universal approach has been adopted for sample size considerations in GMM and this will be used in an exploratory aim; however, our n-to-items ratio exceeds sample size recommendations for related approaches (10-20:1).[107] In sum, the proposed sample size of 264 couples is on par with our previous trials and will allow us to detect clinically meaningful change and address study aims. To insulate the sample size against an estimated attrition of 10% across the study period, 294 couples will be randomized. The attrition estimate is more conservative than our prior trial of *Exercising Together* where no couples in the exercise program dropped out and the drop out in our current GET FIT trial that average 6% for a 6-month intervention. Couples will be enrolled into 10 waves (a new wave begins every 3-4 months) of 9-10 couples to maintain reasonable class sizes and make efficient use of testing resources. We will recruit approximately even numbers of couples coping with each type of cancer (N=98 per disease site) and stratify by cancer type at randomization.

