Aim 1: Determine the efficacy of partnered strength training on relationship quality (intimacy, communication and incongruence). A longitudinal multivariate-outcomes dyad model will be used to directly examine couple trajectories in intimacy (emotional & physical) and communication over time. This is a multi-level model where responses from the survivor and spouse/partner are modeled simultaneously to control for the interdependent nature of the data and autocorrelation among repeated assessments. These models have been described and used extensively by Co-PI [name].[22, 111-113] The Level 1 model has four coefficients representing intercepts (baseline assessments) and slopes (rates of change) for survivors and spouses/partners that become outcome variables in a Level 2 model. Models with linear and quadratic change across time will be compared to determine best fit to the data. Aim 1 will be addressed with Level-2 models that include dummy variables to directly examine the effects of the partnered intervention vs. supervised individual (dummy 1) and unsupervised individual (dummy 2) exercise groups on individual level changes (controlling for couple effects) in intimacy and communication across time. A significant group coefficient on the slopes at level 2 and significantly better fitting model (evidenced by deviance statistic) will indicate the rate of change across time is different depending on a treatment group (i.e., interaction effect). We will also explore the efficacy of *Exercising Together* on incongruence (regarding survivor pain & fatigue) in couples. Univariate-outcomes models will be used to generate Empirical Bayes estimates of the gap between survivor and spouse/partner over time for each symptom measure. This comprehensive approach to estimating incongruence has been described elsewhere[114-116] and successfully used by this team.[55, 63, 113, 117, 118] The effect of *Exercising Together* on incongruence will be directly tested (similar to above model) by a significant coefficient for one of the two GROUP variables on the slope parameter and significantly better fitting model.

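### The text schedules emotional intimacy (DAS), a primary outcome, at 0, 3, 6 and 12 months, but both Schedules of Events mark it at baseline only

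*Combined protocol and SAP*

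**What the plan says.** Section 3.0, Measures and Data Collection, lists emotional intimacy as primary outcome 2, "Measured by the Dyadic Adjustment Scale (DAS) to assess each partner's satisfaction with their relationship", with a time frame of baseline, 3, 6 and 12 months. The same section sets a general rule: "All measures are completed by both members of the couple at each wave".

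Other parts of the document also expect repeated collection:

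- Section 3.0, Six-Month Follow-Up Period: "We will also repeat all measures at month 12".
- Section 3.0, remote-testing list: "All surveys (see 1-5 above, under Primary Outcome Measures" are to go on being sent electronically. This supports repeat collection but gives no visit times of its own.
- Section 8.0, Screening tests and procedures: the testing session, which includes the questionnaires, "will be repeated at 3, 6, & 12 months and only take 1-2 hours".
- Section 13.0, Power and Sample Size, which sizes the trial on the Aim 1 outcomes: "a sample of 264 couples measured 4 times over a 12-month period has a power of 0.80".
- Section 13.0, Analysis Plan, Aim 1: the model is to "directly examine couple trajectories in intimacy (emotional & physical) and communication over time".

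Against this, the row "Emotional intimacy - DAS" in the section 8.0 Schedule of Events has a single mark, under Baseline Testing. The ancillary Schedule has the same row with the same single mark. Neither table explains it.

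**The concern.** The two instructions cannot both be followed. Staff and survey builders would naturally use a visit-by-visit table to decide which instruments go out at each visit, and the protocol gives no order of precedence between table and text.

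If the table was used, a primary outcome has no post-baseline data. The Aim 1 comparison of change between arms, and the Aim 3 comparison of the training and follow-up periods, would then be impossible for emotional intimacy. A later correction of the table would not recover visits that have already passed. The maximum-likelihood handling of missing data in the Analysis Plan could not help either, because no participant would contribute any information on change.

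**Working it through.** **Step 1. Compare the marks.** Instruments for the five primary outcomes, with the number of testing visits marked:

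| Primary outcome | Row in the Schedule | Time points in section 3.0 | Marks, parent Schedule | Marks, ancillary Schedule |
|---|---|---|---|---|
| 1 Dyadic coping | Dyadic Coping | 4 | 4 | 4 |
| 2 Emotional intimacy | DAS | 4 | **1** | **1** |
| 3 Physical intimacy | Physical Intimacy Behavior Scale | 4 | 4 | 4 |
| 4 Concealment of symptoms | EIDB Scale | 4 | 4 | 4 |
| 5 Symptom incongruence | BPI; FACIT; SF-36 (within the quality-of-life row) | 4 | 4 each | 4 each |

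The DAS is the only primary-outcome instrument without follow-up marks. A damaged table is an unlikely explanation: the rows directly above and below are intact with marks in the right columns, and the same single mark appears in two separate tables. Among the baseline assessments the only other baseline-only row is Demographics.

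**Step 2. Count what is at stake in the parent trial.** Inputs from section 13.0: 264 couples needed, 10% attrition, 294 randomized.

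- Check of the plan's figure: 264 / (1 − 0.10) = 293.3, rounded up to 294. It reproduces.
- Participants: 294 × 2 = 588. By the text, 588 × 4 = 2,352 DAS records; by the Schedule, 588 × 1 = 588.
- Difference before attrition: 3 × 588 = 1,764.
- Difference for the 264 couples left after attrition: 264 × 2 = 528, and 3 × 528 = 1,584.

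**Step 3. Check whether the Aim 1 model can be fitted.** The Analysis Plan gives each partner an intercept and a slope, and each of these depends on two group dummies. For one partner the fixed-effect columns are 1, D1, D2, t, t·D1 and t·D2. Two partners give 2 × 6 = 12 columns.

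- With t = 0, 3, 6, 12: mean 5.25, and the sum of squared deviations is 27.5625 + 5.0625 + 0.5625 + 45.5625 = 78.75. The rank is 12 of 12. With quadratic terms added it is 18 of 18.
- With t = 0 only: the sum of squared deviations is 0 and every column containing t is zero. The rank is 6 of 12, or 6 of 18 in the quadratic version. All 6 slope and group-by-slope terms of the linear model are unidentified.

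The rank does not depend on the number of couples; it was the same at 264, 294 and 3,000. Within a couple, baseline-only collection gives 2 observations for the 4 Level 1 coefficients, against 8 observations with four visits.

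The stated power of 0.80 was not reproduced, because the variance components are not given. The point does not depend on it.

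**The case against.** The strongest reply is that the document largely settles the matter itself. An explicit time frame, a rule covering all measures, the month-12 statement, the repeated testing session and the Aim 1 model all point to four assessments; one table row and its near-copy point the other way. The ancillary table resembles the parent table so closely that it would inherit any slip, so it is weak corroboration. The Schedule is also visibly a summary: it has no row for weight and height, and it marks the loneliness scale without the restriction to newly enrolled participants that section 3.0 states. Surveys go out as links from one study team, so the text may well have governed in practice. Finally, the harm is conditional, and the rank calculation shows only that one time point cannot give a slope; it says nothing about how likely that situation is.

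Most of this stands. The row is probably an omission, the harm is conditional, and the four measurements in the power statement are a general assumption rather than a statement about the DAS. What the reply does not do is remove the contradiction. No passage ranks text above table, and the documents do not show how the survey system was built, so they cannot establish that the DAS was sent after baseline.

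**Conclusion.** The contradiction is real and must be fixed. It affects one of the five primary outcomes.

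Its size depends on a fact outside the documents. If the text was followed, the loss is zero. If the Schedule was followed, three of four DAS assessments per participant are missing (at most 1,764 before attrition, 1,584 at the planned completing sample), and no between-arm difference in change can be estimated for emotional intimacy under Aim 1 or Aim 3. The other four primary outcomes keep all four visits in either case.

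The statistical damage, if any, comes from the parent Schedule. The ancillary study is a feasibility pilot whose data are not combined with the parent trial, and no planned efficacy analysis there uses the DAS.

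**What to change.** - Add marks at 3, 6 and 12 months to the DAS row in the parent Schedule of Events, and make the same change in the ancillary Schedule for consistency.
- Confirm that the survey build sends the DAS to both partners at those visits.
- Check whether follow-up DAS data exist for couples already past those visits, and report any gap.
- If baseline-only collection was intended, change the time frame of primary outcome 2 in section 3.0 and remove or replace the trajectory analysis of emotional intimacy in section 13.0.
- In the same edit, the Demographics row (baseline only) can be reconciled with Descriptive Measures in section 3.0, which says those variables are updated at later visits. This is minor.

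The cost is a table correction in the next amendment plus one check of the survey build and the data held. No new visit is needed, because other surveys are already scheduled at 3, 6 and 12 months.

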## Ancillary study: SCHEDULE OF EVENTS

Procedures	Eligibility Screening	Baseline Testing	Intervention	3-Month Testing	6-Month Testing	9-Month check-in	12-Month Testing	Monthly - Month 1 – 12
Pre-screening eligibility	X							
Consent form	X							
Exercise (intervention)			X					
Dyadic Coping		X		X	X		X	
Emotional intimacy - DAS		X						
Concealment of symptoms – EIDB Scale		X		X	X		X	
Physical intimacy – The Physical Intimacy Behavior Scale		X		X	X		X	
Pain - BPI		X		X	X		X	
Fatigue - FACIT		X		X	X		X	
Depressive symptoms – CES-D		X		X	X		X	
PROMIS Anxiety		X		X	X		X	
Fear of recurrence – F.O.R. scale		X		X	X		X	
Demographics – demographic questionnaire		X						
Comorbidities – Charlson Comorbidity Index		X		X	X		X	
Shared activities		X		X	X		X	
Physical activity - CHAMPS		X		X	X		X	
Quality of Life – QLQ-C30 & SF-36		X		X	X		X	
Sexual Satisfaction – PROMIS Sexual Satisfaction Survey		X		X	X		X	
Care strain – Role Overload; Multidimensional caregiver strain index (MCSI)		X		X	X		X	
Cancer-related Loneliness – Cancer Loneliness Scale		X		X	X		X	
Post-Intervention Survey					X			
Exercise Follow-up Survey						X	X	
Adverse Event Survey								X
Physical functioning-PPB		X		X	X		X	
Push-up test		X		X	X		X	
Plank test		X		X	X		X	

